### **9.5 Treatments**

#### **9.5.1 Treatment Assignment**

This is an open-label, non-randomized study therefore the study site personnel, sponsor and patient will all know the treatment.

The treatment assignment is coordinated centrally by the Sponsor.

After the investigator/study site identifies a potential patient, the investigator/study site should notify sponsor of potential patient by sending a Screening Notification email to the Study Manager and Medical Monitor. Formal screening procedures should not begin until a slot has been confirmed for any potential patient. The Sponsor will confirm that the patient is held a spot for potential treatment.

At any time, the study can end prior to the potential patient getting dosed.

#### **9.5.2 Treatments Administered**

##### **Methotrexate**

During the MTX Run-in Period, which begins 4 weeks prior to the first dose of pegloticase, subjects will take oral MTX at a dose of 15 mg weekly.

Subjects will be instructed to take MTX weekly on the same day each week (if dosing more frequently than once in a day (i.e. BID, TID), the total weekly MTX dose should be taken within

24 hours, preferably the same calendar day) and record the date and time of each dose in the dosing calendar.

During the MTX Run-in Period, if a dose is missed, it should be taken as soon as it is remembered. If it is within 48 hours of the next scheduled dose, the subject will be instructed to skip the missed dose and resume at the next regularly scheduled time; thus, subjects will be instructed not to double a dose to make up for a missed dose if within 48 hours of the next dose. Investigators may choose to have subjects take the weekly dose divided over the day (i.e. BID, TID).

During the Pegloticase + MTX Period, MTX should be taken 1 to 3 days prior to the pegloticase infusion and one additional weekly dose after the last infusion (at Week 22) for subjects who have not stopped pegloticase due to study sUA Discontinuation Criteria. If a subject is not able to take the MTX 1 to 3 days prior to the pegloticase infusion, MTX must be taken  $\geq$ 60 minutes prior to the pegloticase infusion.

During the Pegloticase + MTX Period, if a subject becomes unable to tolerate the MTX the dosage may be decreased.

Subjects will also take folic acid 1 mg orally every day beginning at Week -4 (the start of MTX) until prior to the Week 24 Visit.

### **Pegloticase**

All subjects who meet the inclusion/exclusion criteria and tolerate oral MTX 15 mg weekly during the MTX Run-in Period will receive pegloticase at a dose of 8 mg administered IV every 2 weeks for a total of 12 infusions from Day 1 through Week 22 inclusive (Pegloticase + MTX Period). The date and start and stop time of infusion will be recorded. Subjects will not be fasting on the day of infusion and will be encouraged to have a snack or normal meal before or after the infusion.

All subjects will receive standardized prophylactic treatment to reduce the risk of acute gout flares, beginning  $\geq$ 1 week before the first dose of pegloticase and continuing flare prophylaxis throughout the pegloticase treatment period per American College of Rheumatology guidelines [Khanna D et al. 2012].

Standardized IR prophylaxis consisting of pre-treatment with an antihistamine, acetaminophen and a corticosteroid will accompany each infusion.

#### **9.5.2.1 Folic Acid**

Subjects will take folic acid 1 mg orally every day beginning at Week -4 (the start of MTX) until prior to the Week 24/End of Study/Early Termination Visit.

If the subject discontinues pegloticase due to the sUA Discontinuation Criteria or other reason, MTX and folic acid should also be discontinued.

Prescriptions are to be filled at a local pharmacy, as needed. At study visits, the subject will be asked a Yes/No question whether folic acid was taken per protocol.

### **9.5.2.2 Gout Flare Prophylaxis**

It is required that before a subject begins the Pegloticase + MTX Period, he or she has been taking at least one protocol standard gout flare prophylaxis regimen (i.e. colchicine and/or NSAIDs and/or lowdose prednisone  $\leq 10$  mg/day) for  $\geq 1$  week before the first dose of pegloticase and continuing flare prophylaxis throughout the pegloticase treatment period per American College of Rheumatology guidelines [Khanna D et al. 2012].

Prescriptions are to be filled at a local pharmacy, as needed. At study visits, the subject will be asked a Yes/No question whether gout flare prophylaxis was taken per protocol.

### **9.5.2.3 Infusion Reaction Prophylaxis**

Since IRs can occur with pegloticase, all subjects will receive IR prophylaxis prior to each infusion, consisting of an antihistamine, acetaminophen and a corticosteroid. To standardize this regimen, subjects will receive fexofenadine (180 mg orally) the day before each infusion; fexofenadine (180 mg orally) and acetaminophen (1000 mg orally) the morning of each infusion; and methylprednisolone (125 mg IV) given over an infusion duration between 10 - 30 minutes, immediately prior to each infusion. Substitution of the corticosteroid is not allowed. The name, dose, route, date and time of administration of each prophylactic medication will be recorded in the medical record and in the eCRF. The Solumedrol used for IR prophylaxis will be supplied by the site. Other IR medications administered prior to each infusion may also be supplied by the site.

NOTE: If subject's HbA1c is  $>6.5\%$  at Screening and/or if subject has known diagnosis of diabetes mellitus, the pre-infusion IV steroid dose may be reduced (e.g., methylprednisolone 75 mg IV) after consulting with the Horizon Medical Monitor.

Prescriptions are to be filled at a local pharmacy, as needed. At study visits, the subject will be asked a Yes/No question whether IR prophylaxis was taken per protocol.

As a precaution, emergency equipment will be readily available to treat a possible hypersensitivity reaction and will include drugs that would be used to treat an anaphylactic reaction. Personnel trained in managing IRs and, in the use of the emergency equipment will be readily available during and for 1 hour after, the infusion. As IRs can occur after the completion of the infusion, subjects will be observed for 1 hour post-infusion.

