In the phase 3 pivotal studies, deaths, AEs, SAEs, as well as the laboratory abnormalities were generally equally distributed across placebo and pegloticase treatment groups, with the clear exception of gout flares and IRs. Pegloticase-treated subjects exhibited a higher rate of gout flares during Months 1-3 as uric acid was being acutely lowered, then a decrease in gout flares vs. placebo during Months 4-6. Despite use of prophylactic medications against hypersensitivity including administration of corticosteroids, antihistamine and acetaminophen in advance of each pegloticase infusion, IRs were seen in 22/85 (26%) of subjects receiving the 8 mg 2 week regimen. There was no specified definition of anaphylaxis in the Phase 3 protocols and there were no investigator-reported events of anaphylaxis in the Phase 3 studies with pegloticase. However, in a post-hoc review applying the NIAID/FAAN criteria (Sampson et al., 2006), it was determined that across the Phase 2 and Phase 3 program, anaphylaxis occurred in 6.5% of subjects treated with pegloticase dosed every 2 weeks. Anaphylaxis generally occurred within 2 hours after treatment. Manifestations included wheezing, peri-oral or lingual edema, or hemodynamic instability, with or without rash or urticaria. All of these events had relatively rapid resolution with the cessation of infusion.

In a post-hoc analysis, the apparent role of immunogenicity in both loss of urate lowering effect and incidence of IRs was appreciated. Only 2% of subjects with anti pegloticase antibody titers exceeding 1:2430 maintained a urate-lowering response to pegloticase compared with 63% of subjects who were treated for at least 2 months without developing high-titer antibodies ( $p < 0.001$ ) (Sundy et al., 2011). The incidence of IRs was higher among subjects who developed high-titer antibodies compared with those who had titers that did not exceed 1:2430 (60% vs 19%;  $p < 0.001$ ) (Sundy et al., 2011). In addition, most IRs occurred when sUA levels were greater than 6 mg/dL. Retrospective analyses showed that the loss of urate-lowering efficacy, as reflected by sUA of greater than 6 mg/dL, preceded a patient's first IR, whenever it occurred, in 20 (91%) of 22 subjects treated with pegloticase every 2 weeks.

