#### **9.5.7.3.2.3 Gout Flare Treatment**

An increase in gout flares is frequently observed upon initiation of urate lowering treatment (ULT), including pegloticase. Subjects will be instructed to contact the site within 12 hours of the onset of symptoms. Gout flares will be confirmed through questioning or direct observation, as detailed in Section 9.6.1.10. All subjects who experience a gout flare during the study will be prescribed anti-inflammatory treatment (e.g., corticosteroids, colchicine and intra-articular steroid injections), as is clinically indicated or deemed necessary on an individual basis at the discretion of the investigator (Becker, 2019). Pain medications for gout flare should be administered according to standard of care as is clinically indicated or deemed necessary on an individual basis at the discretion of the investigator. All medications should be documented on the concomitant medication eCRF.

Colchicine can be prescribed. The precise dose and regimen of colchicine should be individualized for each subject based on renal function and gastrointestinal intolerance by the Investigator and documented on the concomitant medication eCRF.

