#### **9.5.7.3.2.4 Infusion Reaction Treatment**

Subjects must be monitored closely for signs and symptoms of IRs. In the event of an IR, the infusion should be slowed, or stopped and restarted at a slower rate at the discretion of the Investigator. If a serious IR occurs, the infusion should be discontinued and treatment should be provided, as needed.

If a subject experiences an AE suspected to be an IR:

- A physical examination will be performed to capture medically relevant details, including, but not limited to, a thorough dermatologic examination for detection of erythema, urticaria (hives), or peri-oral or lingual edema; a chest examination for breath sounds, stridor or wheezing; and a cardiac examination with attention to irregular heartbeat.
- Vital signs (sitting or supine BP, heart rate, respiratory rate and body temperature) will be captured at least every 30 minutes until the resolution or stabilization of the AE.
- A 12-lead ECG will be performed.
- A serum sample will be collected in a serum-separating tube at that time or at the subsequent visit. The sample will be centrifuged, frozen at -20°C or colder and stored for the batch shipment to a Horizon designated laboratory for evaluation of pegloticase antibodies at a future date.

If, in the Investigator's opinion, the subject is experiencing an anaphylactic reaction (see Section 9.6.1.2.1.5), pegloticase should be immediately discontinued. Any incidence of anaphylaxis should be reported as an SAE.

The Investigator may administer any medically indicated pharmacologic agent or procedure intended to relieve symptoms (CAUTION: no other drugs can be mixed in the pegloticase infusion bag). Signs and symptoms of the AE and drugs given for treatment are to be recorded in the medical record and in the eCRF.

After the first incidence of an IR that does not meet the criteria of anaphylaxis (see Section 9.6.1.2.1.5) or does not meet serious criteria, the Investigator may elect to initiate the next infusion at a slower rate. Additionally, the Investigator may choose to prescribe prednisone (e.g. 20 mg) to be taken in the morning of the next infusion. All changes to infusion rate or dilution and drugs given for prophylaxis or treatment, are to be recorded in the medical record and in the eCRF.

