#### **Infusion Reaction**

An IR will be defined as any infusion-related AE or cluster of temporally-related AEs, not attributable to another cause, which occur during the pegloticase infusion and for 2 hours post infusion. Other AEs that occur outside of the 2 hour window following the infusion may also be

categorized as an IR at the Principal Investigator's discretion. Signs and symptoms of the IR and treatments administered will be documented in the medical record and in the eCRF. Examples of AEs not considered possible IRs include, but are not limited to: laboratory abnormalities that are unlikely to have occurred during or within 2 hour following the infusion (e.g., anemia), gout flares, most infectious diseases, or the recurrence or worsening of a known chronic medical problem identified in the subject's medical history.

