#### **9.6.1.2.2 Documentation of Adverse Events**

AE and SAE monitoring will begin from the signature of the ICF until the 3-month Post-Treatment Follow-up Visit.

Subjects will be questioned about AEs at each study visit, using nonspecific questions, such as “How have you been feeling since the last study visit?” AEs must be recorded on the AE eCRF and documented in the source record after the signing of the ICF.

AEs recorded before the first dose of MTX in the Run-In Period will be recorded as medical history.

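### The infusion reaction (IR) window runs to 2 hours after infusion but required observation ends at 1 hour, and later IRs are sought only by a nonspecific question at the next visit, so the primary IR proportion may be underestimated by an unknown amount.

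*Protocol*

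**What the plan says.** Protocol 9.6.1.2.1.5 (Infusion Reaction) defines IRs as infusion-related events not attributable to another cause "which occur during the pegloticase infusion and for 2 hours post infusion". The window is not closed at that point: "Other AEs that occur outside of the 2 hour window following the infusion may also be" counted as IRs if the Principal Investigator so judges.

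Protocol 9.5.2.3 notes that IRs can follow the end of the infusion and sets the observation period: "subjects will be observed for 1 hour post-infusion". Staffing covers the same hour: "Personnel trained in managing IRs and, in the use of the emergency equipment will be readily available during and for 1 hour after" the infusion.

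For AEs generally, Protocol 9.6.1.2.2 says: "Subjects will be questioned about AEs at each study visit, using nonspecific questions". Infusion visits are every two weeks.

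SAP 3.4.1 counts subjects with an adjudicated IR of any grade from Day 1 to Week 24 and declares the endpoint met if the upper limit of the two-sided 95% exact interval is below 13%.

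**The concern.** The second hour of the endpoint's own window has no required observation. I found no diary, next-day call or instruction to report IR symptoms after leaving the site. Gout flares do have such an instruction (Protocol 9.5.7.3.2.3): "Subjects will be instructed to contact the site within 12 hours of the onset of symptoms". Post-infusion PK sampling (Protocol 9.6.3) may take place any time from 15 minutes to 2 hours after the infusion, and only at selected visits, so it does not keep subjects on site for the second hour.

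The endpoint counts IRs of every grade. A mild, brief reaction on the way home is the kind most easily left out when a subject is asked, two weeks later, a general question about how they have been. Adjudication can reclassify a reported event but cannot recover one that was never reported. A subject missed in this way lowers the primary proportion, which is the direction that favours success.

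**Working it through.** **Inputs.** n = 110, an expected IR rate of 5.0% and a stated probability above 80% (Protocol 9.7.9; SAP 1.1.3). Two-sided 95% Clopper-Pearson interval and the 13% limit (SAP 3.4.1).

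**1. The success limit.** The upper bound for x subjects with an IR is the 0.975 quantile of Beta(x+1, n−x).

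- x = 6: 11.49%
- x = 7: 12.67%, met
- x = 8: 13.83%, not met

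The rule is therefore met when x ≤ 7 of 110.

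**2. The plan's own figure.** P(X ≤ 7) for X ~ Bin(110, 0.05) is 81.4%. This agrees with the stated value above 80%, provided 5% is read as the true rate; the text calls it the observed rate. The sample-size figure is not in dispute.

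**3. Effect of missed subjects.** The documents do not say what share of IRs begin after the first hour, or what share go unreported. Let m be an assumed share of subjects with an IR in whom no IR is ever recorded. The recorded count is then Bin(110, p(1−m)), and the chance of meeting the rule is P(X ≤ 7). For example, p = 0.08 and m = 0.10 give a recorded rate of 0.08 × 0.90 = 0.072 and a chance of 46%.

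| True rate p | m = 0 | m = 5% | m = 10% | m = 30% |
|---|---|---|---|---|
| 5% | 81% | 85% | 88% | 96% |
| 8% | 34% | 40% | 46% | 73% |
| 13% | 2.0% | 3.1% | 4.8% | 20.6% |

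The values of m are assumptions chosen to show a range, not estimates.

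**4. Unit of m.** The endpoint counts subjects with any IR over up to 12 infusions. A subject drops out of the count only if every one of that subject's IRs goes unrecorded. The share of subjects missed is therefore at most the share of events missed when misses are spread evenly, and smaller where subjects have repeated IRs. The table should not be read as a per-event miss rate.

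**The case against.** Late IRs are foreseen and are not excluded. The investigator may classify events beyond 2 hours as IRs, and SAP 3.6.3.4 tabulates onset at more than 2 to 24 hours and at more than 24 hours. Protocol 9.5.7.3.2.4 allows for a suspected IR that comes to light late: "A serum sample will be collected in a serum-separating tube at that time or at the subsequent visit". AEs of special interest have their own eCRF, and subjects are asked about AEs at every visit, so recall is prompted, if only in general terms. Protocol 7.1.2 says of earlier studies "Anaphylaxis generally occurred within 2 hours after treatment", but that concerns anaphylaxis, which must be reported as an SAE and is the reaction least likely to be lost. Severe reactions in general are unlikely to go unmentioned.

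All of this stands, and it limits the point to mild reactions after discharge. It does not remove the point: these provisions show that the plan wants late IRs counted, but none adds a way of finding them beyond the general question.

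A reader might infer that the problem grows as the infusion shortens, because time under observation from the start of infusion falls from 60 + 60 = 120 minutes to 45 + 60 = 105 and 30 + 60 = 90 across the three cohorts. The documents do not support this. The IR window is anchored to the end of the infusion, so the unobserved hour is the same in every cohort. A gradient would require reactions at a fixed delay from the start of infusion, which no section states.

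**Conclusion.** The two sections do not match, and post-discharge ascertainment is passive. The primary IR proportion may therefore be underestimated by an unknown amount, in the direction that favours the 13% rule. A reader might go further and say that the rate is biased low; the documents show a risk of under-ascertainment, not a demonstrated bias, because they give neither the share of IRs starting after the first hour nor the share unreported.

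The result is sensitive because one subject can decide it (7/110 against 8/110). If the true rate is the planned 5%, the consequence is modest: on the assumed values of m, a chance of success that is already 81% rises to 85–96%. It matters more at 8%, where 34% becomes 40–73%, and at 13%, where 2.0% becomes 3.1–20.6%. These figures rest on the assumed values of m, a common m for all subjects, and independence between subjects. No claim is made that the effect differs by infusion duration.

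**What to change.** 1. Reconcile the observation period in Protocol 9.5.2.3 with the IR window in 9.6.1.2.1.5, and state how IR symptoms after discharge are to be ascertained. Which period is right is a clinical decision and none is proposed here.

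2. In Protocol 9.6.1.2.2, add a scripted item at each visit that follows an infusion: any symptoms between leaving the site and 24 hours after the last infusion, with time of onset. Send positive answers to the existing eCRF for AEs of special interest and to adjudication. The 24-hour limit matches a timing category already in SAP 3.6.3.4, and recorded onset times would reduce entries in its missing category.

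**Cost.** The item uses visits that already take place. It will bring in some non-specific reports to adjudicate, and Protocol 9.8 requires a formal amendment with IRB approval. Subjects treated before and after the change would be ascertained differently; this should be stated when the result is reported or set against the 5% from the earlier trial.

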### **9.5.3 Identity of Investigational Products**

#### **9.5.3.1 Pegloticase**

##### 8 mg/mL Uricase:

Pegloticase is a clear, colorless, sterile solution in phosphate-buffered saline intended for IV infusion after dilution. Each mL of pegloticase contains 8 mg of uricase protein conjugated to 24 mg of 10 kDa monomethoxypoly(ethylene glycol). Excipients include disodium hydrogen phosphate dihydrate, sodium chloride, sodium dihydrogen phosphate dihydrate and water for injection.

#### 0.16 mg/ml Uricase:

Pegloticase is a clear, colorless, sterile solution in phosphate-buffered saline provided for ready-to-use for IV infusion. 50 mL of pegloticase contains 8 mg of uricase protein conjugated to 24 mg of 10 kDa monomethoxypoly (ethylene glycol). Excipients include disodium hydrogen phosphate dihydrate, sodium chloride, sodium dihydrogen phosphate dihydrate and water for injection.

#### **9.5.3.2 Methotrexate**

MTX 2.5 mg tablets for oral administration will be provided to subjects as a commercially available generic (MTX Full Prescribing Information).

A dosing calendar will be provided to subjects at the Week -4 Visit to record each dose of MTX and the date and time of each dose on each calendar day of MTX administration. Additional calendar pages may be provided on future visits as needed.

#### **9.5.4 Labeling**

Pegloticase (KRYSTEXXA) is commercially available as 8 mg/mL uricase in the United States and will be supplied by PCI Pharma Services packaged in sterile, single-use 2-mL glass vials with coated (latex-free) rubber injection stopper to deliver pegloticase as 8 mg of uricase protein in 1 mL volume. An ancillary label will be fixed to the vial and carton that identifies the study, allows subject information to be entered and contains the investigational use caution statement according to the FDA Title 21 CFR Part 312 requirements. Each vial label will have a unique number.

The alternative ready-to-use presentation of pegloticase (0.16 mg/ml uricase) will be supplied by PCI Pharma Services packaged sterile, single-use 50-mL glass vials with a Fluorotec-coated rubber injection stopper which delivers 8 mg uricase in a 50 mL solution. An ancillary label will be fixed to the vial and carton that identifies the study, allows subject information to be entered and contains the investigational use caution statement according to the FDA Title 21 CFR Part 312 requirements. Each vial label will have a unique number.

MTX will be provided to sites by PCI Pharma Services as tablets in bottles. An ancillary label will be fixed to the bottle that identifies the study, allows subject information to be entered and contains the investigational use caution statement according to the FDA Title 21 CFR Part 312 requirements. Each bottle label will have a unique number. Bottles will be provided to study subjects after the Week -4 Visit for weekly dosing after visit procedures and inclusion/exclusion criteria are confirmed.

